iPhone® Helping Evaluate Atrial fibrillation Rhythm through Technology (iHEART) Study (NCT02731326)

IRB approval: August 15, 2020

Study Design

The iPhone® Helping Evaluate Atrial fibrillation Rhythm through Technology (iHEART) study is a single-center, prospective, randomized controlled trial (RCT) (**Figure 1**). The primary aims of the iHEART study are to: (1) Examine the efficacy of mHealth ECG technology (iHEART intervention) on the detection and treatment of recurrent AF as compared to usual cardiac care (control group); (2) Evaluate the quality-adjusted life-years (QALYs) in those in the iHEART intervention as compared to the control group between baseline and 6 months; (3) Determine the impact of behavior altering, motivational text messages on chronic cardiovascular conditions (e.g., hypertension, diabetes) and AF knowledge over 6 months. Participants are randomized to one of two groups: iHEART (intervention group) or usual care (control group). All participants enrolled will be followed for a period of 6 months. This study protocol adheres to the appropriate standards of reporting as stated in the Standard Protocol Items: Recommendations for Interventional Trials statement and facilitates the methodology of the Consolidated Standards of Reporting Trials statement for later dissemination of the results of the outlined RCT.

Study Population

Patients will be screened for eligibility (**Table 1**). Those who meet inclusion criteria will be approached for enrollment after the patient's provider agrees to the study protocol and is willing to receive and review ECG transmissions. The details of the study will be explained in English or Spanish, and patients will be given an opportunity to ask questions before signing informed consent. A copy of the consent form will be given to the patient.

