Upon study entry, all relevant clinical data will be collected at baseline and monthly throughout six months via an electronic medical records system review. This will be used to capture and quantify cardiac outcomes in both groups. In addition, all outside medical records will be requested, and participants will be contacted monthly to capture any hospitalizations, cardiac events, or changes in therapy that may occur outside of our center and clinics. AF in the usual care group may be detected during routine follow-ups with providers, as well as during self-evaluations such as a pulse check initiated as a result of participant-reported symptoms or changes in health status. AF may also be captured by a 12-lead ECG, pulse check, or heart sound auscultation during an exam that reveals an irregular heart rhythm. Participants in the usual care group may seek medical evaluation by their providers because of a change in their health status or symptoms (shortness of breath, palpitations, fatigue), which may lead to further cardiac monitoring or testing (e.g., echocardiogram) that may reveal AF. This could include Holter monitoring (24 hour) or extended cardiac monitoring (7-30 days) that may document AF and be the basis for changes in treatments prescribed by their providers (e.g., medication changes or dosage adjustments, cardioversion). In the intervention group, AliveCor® Mobile ECG transmissions will be read daily to detect recurrence of AF or other arrhythmias. All results and any treatment changes due to mobile ECG findings will be recorded over the course of the study period.

All study participants will be asked to complete a series of questionnaires including the Atrial Fibrillation Knowledge Scale (AFKS), the Canadian Cardiovascular Society Severity in Atrial Fibrillation scale (CCS-SAF), the Atrial Fibrillation Effect on Quality of Life (AFEQT), the Control Attitudes Scale-Revised (CAS-R), the Morisky 4-item Self-Report Measure of Medication-Taking Behavior (MMAS-4), the Self-Efficacy for Appropriate Medication Use Scale (SEAMS), the Short Form Health Survey (SF-36 Quality of Life), European Questionnaire 5 Dimensions (EQ-5D), the Patient Health Questionnaire (PHQ-9), and the State Trait Anxiety Inventory (STAI). These measures will be administered to both the intervention and control groups at baseline prior to any procedures, such as a cardioversion or ablation, and again at the 6-month follow-up visit for the purpose of comparison.

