The primary endpoint is detection of recurrence of AF. Secondary endpoints include treatment changes as a result of early detection of AF recurrence, study questionnaire scores at baseline and six months, including QoL, QALYs, and improvement in cardiovascular measures (e.g., blood pressure, glucose levels) and AF knowledge from baseline to 6 months. Outcome assessors will be blinded to group allocation.

Statistical Analysis

We will define and calculate recurrent AF detection rate as the ratio of the number of recurrent AF episodes to the number of person-months of follow-ups. We will compare the difference in recurrent AF detection rate over the six-month study period between the control group and the iHEART intervention group. Analysis of the potential moderating effects of demographic factors (e.g., age, gender, etc.) as well as the difference between the groups will be performed using multivariate Poisson regression.

We will compare the time-to-treatment between the iHEART intervention group and the control group with the application of survival analysis methods. For those who are treated for recurrent AF, the time-to-treatment is the time from beginning of study to the time of treatment. Those who are not treated for recurrent AF will be censored at the end of the sixth month, or the time of death should a subject die before the sixth month. We will apply the Cox proportional hazard model to examine and test the difference in the time-to-treatment between the intervention group and control group, with the adjustment for other potential confounders (e.g., age, gender). QALYs are calculated as follows: for each month of life lived at an EQ-5D index of x , the QALYs will be $x/12=0.0833x$ years. We will calculate QALYs during the 6-month study period for all participants by summarizing QALYs from baseline through sixth month. We will compare QALYs between the iHEART intervention group and the control group using a two-tailed independent sample t-test. To adjust for potential confounders (e.g., age, gender), multivariate linear regression models will be used. Additionally, we will compare change of quality of life (QoL) and symptoms of AF scores (AFEQT, AFKS, EQ5D and CCS-SAF scales, etc.) from baseline to 6 months between the two groups and between those with and without AF using linear mixed models (growth model).

Figure 1. Flowchart for Study Procedures

[figure not shown]

Table 1. Inclusion and Exclusion Criteria

Inclusion Criteria

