- Males and females (English or Spanish speaking) age ≥ 18 years with a prior history of AF in the last 30 days that was treated and normal rhythm restored
- Already utilizes a smartphone prior to enrollment
- Ability to successfully use the AliveCor™ Heart Monitor, capture a baseline ECG, and transmit on the day of enrollment
- Demonstrated ability to receive and read text messages on the day of enrollment
- Willingness to complete the study questionnaires at baseline and 6 months

Exclusion Criteria

- Documented permanent (chronic) AF
- Unwillingness to have their clinical data collected over the study period
- Unwillingness to receive and read cardiovascular text messaging three times a week.

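### Time-to-treatment is censored only at month 6 or death, so participants whose status becomes unknown earlier count as untreated to month 6, which biases the secondary hazard ratio if such loss differs by arm

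*Combined protocol and SAP*

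**What the plan says.** The Statistical Analysis section defines the outcome for treated participants: "the time-to-treatment is the time from beginning of study to the time of treatment". For everyone else it gives two possible end times: "Those who are not treated for recurrent AF will be censored at the end of the sixth month, or the time of death". The comparison is by Cox regression, adjusted for factors such as age and gender: "We will apply the Cox proportional hazard model to examine and test the difference in the time-to-treatment between the intervention group and control group".

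The Study end-points section places treatment among the secondary outcomes: "Secondary endpoints include treatment changes as a result of early detection of AF recurrence". Time-to-treatment is not itself named in that list, but it is the analysis that serves it.

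Three other places bear on how often status could become unknown:

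- Study Design states an intention: "All participants enrolled will be followed for a period of 6 months".
- Outcome assessments sets out ascertainment in both groups: "all relevant clinical data will be collected at baseline and monthly throughout six months via an electronic medical records system review". It adds requests for outside records and monthly contact to pick up events and "changes in therapy that may occur outside of our center and clinics".
- Table 1 lists as an exclusion "Unwillingness to have their clinical data collected over the study period".

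No section says how withdrawal, loss to follow-up or unknown treatment status enters the Cox model, and no dropout rate or missing-data method is given.

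**The concern.** A Cox model compares those treated at each moment with those known to be still at risk. The written rule puts every participant without a recorded treatment at risk until month 6 or death. Someone who withdraws consent to data collection at month 1 would contribute five months (6 − 1) in which a treatment could not have been recorded. Those months count as time at risk without an event, so the arm's apparent treatment hazard is too low.

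If both arms have the same share of such participants, the effects nearly cancel. If the shares differ, the hazard ratio moves away from the arm with more loss: up if control loses more, down if intervention loses more. Unequal loss is possible because the arms differ in contact. Intervention participants get a phone, daily ECG review and three texts a week, and control participants get usual care. At stake is the plan's only formal between-group test of treatment timing, which serves the treatment part of its first aim.

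**Working it through.** There is no figure in the plan to reproduce. The 300 participants are stated without an event rate, effect size, power or loss rate. The question is which way and how far the written rule moves the hazard ratio (HR, intervention versus control).

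**Inputs from the document.** 150 per arm, 6 months of follow-up, and the rule in "Those who are not treated for recurrent AF will be censored at the end of the sixth month, or the time of death".

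**Assumed inputs (none is in the document).**
- Treatment hazard λ = 0.05 to 0.08 per month, so the 6-month treatment probability is 1 − exp(−0.30) = 26% to 1 − exp(−0.48) = 38%.
- Exponential loss, independent of treatment, with a share p lost by month 6.
- Capture c: the share of lost participants whose records are nevertheless complete to month 6.

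**Step 1: hand approximation.** The average share of an arm still under contact over the 6 months is m = p / (−ln(1 − p)):
- p = 10%: 0.10/0.1054 = 0.949
- p = 20%: 0.20/0.2231 = 0.896
- p = 30%: 0.30/0.3567 = 0.841

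With capture, the share whose status is known is r = 1 − (1 − c)(1 − m). Under the written rule an arm's apparent hazard is about λr, so the apparent HR is about the true HR × r(intervention)/r(control). At a true HR of 1.0:
- 20%/10% loss (control/intervention), c = 0: 0.949/0.896 = 1.06
- 30%/10%, c = 0: 0.949/0.841 = 1.13
- 30%/10%, c = 0.8: (1 − 0.2 × 0.051)/(1 − 0.2 × 0.159) = 0.990/0.968 = 1.02

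**Step 2: large-sample Cox limit under the written rule**, found by solving the partial-likelihood score numerically:

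| True HR | Loss control/intervention | c = 0% | c = 50% | c = 80% |
|---|---|---|---|---|
| 1.0 | 20%/10% | 1.06 | 1.03 | 1.01 |
| 1.0 | 30%/10% | 1.13-1.14 | 1.06 | 1.02 |
| 1.0 | 10%/30% | 0.88 | 0.94 | 0.98 |
| 1.5 | 30%/10% | 1.69 | 1.59 | 1.53 |
| 1.5 | 10%/30% | 1.31-1.32 | 1.40-1.41 | 1.46 |

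Full capture gives no bias. Equal 20% loss with no capture gives 1.00 for a true 1.0 and about 1.49 for a true 1.5. A separate set of assumptions (control 6-month treatment probability 20-50%, loss 5-25%, no capture) gives similar shifts: about 5-7% for a 10-point difference in loss and 11-13% for a 20-point difference.

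**Step 3: type I error** at nominal 5%, 150 per arm, simulated (Monte Carlo error 0.3-0.4 points). At 30%/10% loss it is 7.7-10.1% with no capture, 5.7-6.0% with 50% capture and 5.1-5.4% with 80%. At 20%/10% with no capture it is 5.7-5.8%.

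**Step 4: what a repair must do.** Three candidates were simulated.
- *Stop at last completed contact and count treatments only up to it.* This returns about 1.00 (0.994-1.006) for a true 1.0.
- *Censor untreated participants at last contact, but count treatments found in records later.* At 30%/10% loss with 80% of later treatments found, a true 1.0 becomes 0.92. The end date must therefore not depend on whether treatment occurred.
- *Carry participants to month 6 because a record review shows no treatment.* If such reviews find only 50% or 80% of treatments after last contact, 30%/10% loss gives 1.06-1.07 or 1.02-1.03. That is essentially the bias of the written rule at the same capture.

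**The case against.** The strongest reply is that a person of unknown status has not been shown to be untreated, so the sentence may not cover them at all. The section also invokes survival methods and measures the primary rate in person-months of follow-up, so a competent analyst might well stop the clock at last observation. That may be what happens, but the plan does not say it. The sentence sorts participants only into treated and not treated, provides for one early exit (death) and no other, and does not carry the person-months wording over to this endpoint.

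The second reply is that ascertainment is good. Record review does not need the participant to respond, outside records are requested, and people unwilling to have data collected are excluded. Much of this stands. Someone who stops responding but whose in-house and outside records are complete is rightly censored at month 6, and at 80% capture the bias is about 2%. These provisions make unknown status rarer, but they set no date for it when it occurs. The exclusion applies at entry and cannot date a later withdrawal.

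It also stands that every loss, hazard and capture rate above is assumed, and that the larger figures need both a 20-point difference in loss and no capture at all.

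**Conclusion.** The gap is real and minor. The written rule gives a wrong risk set for participants whose status becomes unknown before month 6, and the hazard ratio is biased if their share differs by arm. With no record capture the illustrative shift is about 6% at 20%/10% loss and 12-14% for a 20-point difference. At 80% capture the 20-point figure falls to about 2%. These figures assume constant hazards and loss unrelated to treatment.

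A reader might infer more, and the document does not support it:
- **That the trial's hazard ratio is in fact biased, or in a known direction.** No loss rates are given, and nothing shows which arm would lose more.
- **That everyone who stops responding is wrongly handled.** Those with complete records are handled correctly.
- **That the primary result is at risk.** The AF detection rate has its own person-month denominator and does not use this rule.

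**What to change.** Replace the censoring sentence with an end-of-follow-up date defined identically in both arms and without regard to whether treatment occurred: the earliest of month 6, death, withdrawal of consent to data collection, or the last completed monthly contact covering changes in therapy. Count treatments only up to that date, even if a later one comes to light, and censor untreated participants there. Report loss by arm.

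As a sensitivity analysis, extend the date to the last completed record review, but only where in-house records and the requested outside records were both obtained through that date. An in-house review with no entry does not by itself establish known status.

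The cost is a short definition and one date per participant, which the scheduled monthly contacts should supply. Somewhat fewer events are counted. At 30%/10% loss and a true HR of 1.0, if 80% of later treatments would otherwise have surfaced, the count is 70 instead of 76 (λ = 0.05) or 103 instead of 112 (λ = 0.08). That is about 8% fewer (6/76; 9/112), with a standard error about 4-5% larger. The analysis still assumes that censoring is non-informative, and the SAP should say so.

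### The 6-month QALY comparison leaves baseline EQ-5D out of the named covariates; adjusting for it costs nothing and gains precision, alongside a fixed rule for the unmeasured months

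*Combined protocol and SAP*

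**What the plan says.** **Role of QALYs.** The Study Design section makes the QALY comparison primary aim 2. The Study end-points section lists it among the secondary endpoints: "study questionnaire scores at baseline and six months, including QoL, QALYs".

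**Calculation.** The Statistical Analysis section credits x/12 QALYs "for each month of life lived at an EQ-5D index of x". It continues: "We will calculate QALYs during the 6-month study period for all participants" "by summarizing QALYs from baseline through sixth month".

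**Measurement.** Under Outcome assessments, EQ-5D is given at baseline, before any procedure, and at the 6-month visit. Table 1 names the same two times. The monthly contacts are for hospitalizations, cardiac events and therapy changes; EQ-5D is not mentioned.

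**Analysis.** "We will compare QALYs between the iHEART intervention group and the control group using a two-tailed independent sample t-test". Then: "To adjust for potential confounders (e.g., age, gender), multivariate linear regression models will be used". Baseline EQ-5D is neither named nor excluded. Randomization is stratified by age and gender.

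**Deaths.** The section mentions death only when it defines censoring for time-to-treatment: "or the time of death should a subject die before the sixth month". No index is stated for the months lived by participants who die, and no handling of a missing month-6 EQ-5D is stated.

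**The concern.** The formula needs an index for every month lived, but only two are measured. Rules that interpolate, or that carry the baseline score forward, make the baseline score part of each participant's QALY. Randomised treatment cannot have changed that score. In an unadjusted comparison it adds between-person noise, and any chance difference between the arms at baseline passes into the estimated QALY difference. Adjusting for a score that is already collected removes most of this.

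The size of the QALY difference also depends on the rule chosen for the unmeasured months, and adjustment does not settle that. What is at stake is the precision and the interpretability of the result for a stated primary aim.

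**Working it through.** **1. The plan's own figure.** 1/12 = 0.0833, as stated. Six months at a constant index x give 6x/12 = 0.5x. The factor reproduces.

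**2. Effect of the month-filling rule.** Write QALY = w0·x0 + w6·x6, where x0 and x6 are the baseline and month-6 scores. With equal baselines and a month-6 difference d, the QALY difference is w6·d.

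| Rule | w0 | w6 | QALY difference | Example: x0 = 0.70, x6 = 0.80 (assumed) |
|---|---|---|---|---|
| Baseline for months 1-5, month 6 for the last | 5/12 | 1/12 | 0.083d | 0.358 |
| Trapezoid | 0.25 | 0.25 | 0.25d | 0.375 |
| Month 6 carried back | 0 | 0.5 | 0.5d | 0.400 |

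The sixfold range in the fourth column needs no assumption about SD or correlation.

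**3. Variance with and without adjustment.** Assume a common SD s at both times and correlation r. Any gain from age and gender is ignored.
- t-test, per person: s²(w0² + w6² + 2·w0·w6·r)
- Adjusted for baseline EQ-5D: w6²·s²(1-r²)
- Trapezoid: s²(1+r)/8 unadjusted and s²(1-r²)/16 adjusted, so the ratio is (1-r)/2.
- Month 6 carried back: s²/4 and s²(1-r²)/4, so the ratio is 1-r².

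| r | Trapezoid | Month 6 carried back |
|---|---|---|
| 0.3 | 0.35 | 0.91 |
| 0.5 | 0.25 | 0.75 |
| 0.7 | 0.15 | 0.51 |

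**4. One illustrative power scenario.** The 150 per arm is from the Sample Size section. Assumed, because the documents give none of them: s = 0.20, d = 0.05, r = 0.5, two-sided 5%, both scores available for everyone. SE = √(2·variance/150), normal approximation.
- Trapezoid t-test: effect 0.0125, variance 0.0075, SE 0.0100, z = 1.25, power 24%.
- Carry-back t-test: effect 0.025, variance 0.0100, SE 0.0115, z = 2.17, power 58%.
- Adjusted, trapezoid: effect 0.0125, variance 0.001875, SE 0.0050, z = 2.50, power 71%.
- Adjusted, carry-back: effect 0.025, variance 0.0075, SE 0.0100, z = 2.50, power 71%.

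The adjusted z is the same because w6 cancels. This holds only for participants with both scores and under one common rule that gives month 6 some weight. The estimate still differs twofold between these two rules.

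**5. Sensitivity of the power figures** (trapezoid t-test / adjusted, 150 per arm):
- r = 0.3: 27% / 62%; r = 0.7: 22% / 86% (s = 0.20, d = 0.05)
- d = 0.03: 12% / 32%; d = 0.08: 52% / 98% (s = 0.20, r = 0.5)
- s = 0.15: 38% / 92%; s = 0.25: 17% / 52% (d = 0.05, r = 0.5)
- Carry-back at r = 0.3 (s = 0.20, d = 0.05) gains little: 58% / 62%

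**6. Chance baseline imbalance.** With s = 0.20, the SE of the baseline difference between arms is √(2·0.04/150) = 0.023. An imbalance of 0.02 moves the unadjusted trapezoid difference by 0.25 × 0.02 = 0.005. If it persists to month 6 with r = 0.5, the shift is 0.005 × 1.5 = 0.0075. The assumed effect is 0.0125.

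**The case against.** The strongest reply is that nothing here is an error. The t-test is valid, the regression list is open and so allows baseline EQ-5D, and QALYs are listed as a secondary endpoint. This stands as far as it goes: the point is about efficiency and a rule left unstated. It does not remove the case for a costless gain on a stated primary aim.

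It is also fair that the gain depends on the rule. It is large under the trapezoid and modest with month 6 carried back when r is low. Because the baseline score is taken before procedures and randomisation follows rhythm restoration, that score may not describe the early months of follow-up. This weakens the trapezoid as an automatic choice.

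A reader might go further in four ways that the documents do not support:
- *No main QALY analysis is identified.* The label is absent, but the order is readable: the t-test is the comparison and the regression its adjusted version.
- *The result is open to manipulation.* Under the scenario above, t-tests under carry-back and the trapezoid would disagree in about 35% of trials, but this mostly restates the gap between 58% and 24% power. Picking the better of the two rules with no true effect would give a 7.3% type I error. Both figures are hypothetical; nothing in the documents shows such picking.
- *The questionnaire change analyses share the inefficiency.* The plan says "we will compare change of quality of life (QoL) and symptoms of AF scores (AFEQT, AFKS, EQ5D and CCS-SAF scales, etc" and names linear mixed models, but not how they treat baseline. No power loss can be assigned to them. Nor do they test QALYs.
- *The power figures describe this trial.* They rest on an assumed SD, effect and correlation.

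**Conclusion.** The point holds as a recommended improvement, not as a flaw that invalidates the QALY comparison. The t-test is unbiased under randomisation but leaves avoidable noise in the outcome. With equal SDs, adjusting for baseline EQ-5D leaves 15% to 35% of the t-test variance under the trapezoid, and 51% to 91% with month 6 carried back, for r from 0.7 down to 0.3. The rise to 71% power is one assumed scenario and should be cited only as such.

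The missing month-filling rule is a separate gap in detail that belongs in the same revision. Adjustment does not replace the rule, and deaths or missing month-6 scores break the equality of the adjusted tests across rules.

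**What to change.** 1. Make the main QALY analysis a linear regression of QALY on arm, baseline EQ-5D, age and gender (the last two being the stratification factors). Keep the t-test as supportive.
2. Before analysis, state one rule for the index in the months between baseline and month 6; for survivors the trapezoid, 0.25(x0 + x6), is one option. State the timing of the baseline score relative to procedures and randomisation, and justify the rule in that light.
3. State the index used for months lived by participants who die, and how a missing month-6 score is handled.
4. Report one alternative rule as a sensitivity analysis, for example month 6 carried back.

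The cost is SAP wording. All of it uses data the plan already collects, with no added visits or questionnaires.

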Inclusion criteria will include documented AF that has been treated in the last 30 days resulting in the restoration of normal sinus rhythm. The operational definition of AF for this study will include the presence of AF captured by the AliveCor® Mobile ECG, a standard 12 lead ECG, Holter, or any other external recording mechanism that documents AF. Over a six-month period, those individuals with \leq 7 days of AF will be considered paroxysmal, and those with greater than 7 days of continuous AF will be defined as persistent AF per the AHA/ACC/HRS guidelines. The main exclusion criteria for participants include documented permanent (chronic) AF, unwillingness to use technology and have one's clinical data collected over the study period, unwillingness to receive and read cardiovascular text messaging three times a week, and patients who have a documented medical history of cognitive impairment.

Data and Safety Monitoring

The study was approved by the Columbia University Medical Center Institutional Review Board. Participants provide written informed consent prior to enrollment and all data collection procedures are in accordance with the Health Information Portability and Accountability Act regulations.

Sample Size

A total of 300 participants with documented AF who are undergoing clinical treatment of their AF with electrical cardioversion, radiofrequency ablation and/or medical management to restore normal sinus rhythm will be enrolled. After a normal rhythm is restored, participants will be randomized to usual cardiac care (n= 150) or usual cardiac care plus the iHEART intervention (n= 150). The population will be recruited from the Columbia University Medical Center (CUMC) cardiac services and will include English and Spanish speaking participants.

Randomization

The randomization process will be performed by a random computer number generator in a one-to-one block allocation ratio. In order to achieve a balance of applicable participant characteristics in both the intervention and control groups, participants will be stratified based on age and gender.

Outcome assessments

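### Does the quality-of-life contrast by AF status need a stated window and an arm term, given that AF is detected differently in the two arms?

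*Combined protocol and SAP*

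**What the plan says.** The last sentence of the Statistical Analysis section plans two comparisons of score change from baseline to 6 months, "between the two groups and between those with and without AF using linear mixed models (growth model"). It attaches no window and no classing rule to AF status. The six-month window earlier in that section belongs to the detection rate.

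The text under Study Population does say what counts as AF. It begins "The operational definition of AF for this study will include the presence of AF captured by" and lists the smartphone device, 12-lead ECG and Holter, "or any other external recording mechanism that documents AF". Table 1 requires AF in the last 30 days, treated, with normal rhythm restored.

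On how AF is found, the AliveCor section has intervention participants trained to record daily and with symptoms, and Outcome assessments has the transmissions read daily. For controls, "AF in the usual care group may be detected during routine follow-ups with providers", or they may seek evaluation "because of a change in their health status or symptoms (shortness of breath, palpitations, fatigue"). Further testing is possible: "This could include Holter monitoring (24 hour) or extended cardiac monitoring (7-30 days"). In both arms records are reviewed monthly and "participants will be contacted monthly to capture any hospitalizations, cardiac events, or changes in therapy".

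**The concern.** Everyone enters with AF, so the group without AF cannot mean people with no AF history. The most workable reading is recurrence found during follow-up. That makes AF status a post-randomisation variable, and the primary endpoint is itself its detection, so the trial sets out to show that the two arms differ on it.

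Three things could then go wrong.

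- Missed AF in controls sits in the group without AF and dilutes the contrast.
- Control AF that is found through symptoms is likely to be the more symptomatic AF, which pulls the other way on symptom scores.
- If arm affects scores and is left out of the model, part of the arm effect is counted as an AF effect.

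At stake is the reading of an estimated effect of recurrence on quality of life. If one model held both arm and AF status, the randomised comparison would be at stake too.

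**Working it through.** The plan gives no figure for this contrast, so there is none to reproduce. From the documents: two equal arms of 150. Everything else is assumed: true AF effect -10 points on an unnamed scale, the same true recurrence *p* in both arms (30%, 50%, 70%), and detection *d* by arm.

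**Formulas, with no false positives.** Share classed with AF: w = pd. Share of missed AF among those classed without AF: m = p(1-d)/(1-w). Apparent effect: -10(1-m). The arm-adjusted figure weights the two arm effects by w(1-w).

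**Wide gap, 95% v 50%, p = 50%.**

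- Intervention: w = 0.475, m = 0.025/0.525 = 0.048, effect -9.52.
- Control: w = 0.25, m = 0.25/0.75 = 0.333, effect -6.67.
- Pooled without arm: m = (0.025 + 0.25)/(0.525 + 0.75) = 0.216, effect -7.84.
- Adjusted for arm: weights 0.2494 and 0.1875, effect -8.30.

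| Scenario | Recurrence | Intervention | Control | Pooled | Arm-adjusted |
|---|---|---|---|---|---|
| Wide gap, 95% v 50% | 30% | -9.79 | -8.24 | -8.95 | -9.19 |
| | 50% | -9.52 | -6.67 | -7.84 | -8.30 |
| | 70% | -8.96 | -4.62 | -6.09 | -6.76 |
| Narrow gap, 80% v 70% | 30% | -9.21 | -8.86 | -9.03 | -9.04 |
| | 50% | -8.33 | -7.69 | -8.00 | -8.02 |
| | 70% | -6.82 | -5.88 | -6.32 | -6.35 |
| Symptom selection | 30% | -10.16 | -11.76 | -10.49 | -10.78 |
| | 50% | -10.03 | -10.67 | -9.74 | -10.30 |
| | 70% | -9.74 | -9.23 | -8.54 | -9.48 |

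In the symptom-selection rows half of AF is worth -15 and half -5. Controls detect 80% of the first kind and 20% of the second; the intervention arm detects 100% and 90%.

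**How much comes from the difference between arms?** With equal arms, equal recurrence and no arm effect on scores, the pooled contrast depends only on average detection. In the wide gap that is (95% + 50%)/2 = 72.5%. Putting 72.5% in both arms at p = 50% gives m = 0.1375/0.6375 = 0.216 and -7.84, the same pooled figure. The shortfall from -10 is missed AF, which would be there with identical detection in the two arms.

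**What an omitted arm term adds.** The share of any arm effect that leaks into the contrast is the intervention share of those with AF minus its share of those without. At p = 50% in the wide gap this is 0.475/0.725 - 0.525/1.275 = 0.24; in the narrow gap it is 0.05. An arm effect of 0.2 SD therefore leaks about 0.05 SD in the wide gap.

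**Effect on the randomised comparison if AF status is in the same model.** With no true arm effect, the spurious arm coefficient is minus the adjusted AF effect times the difference in w. In the wide gap at p = 50% that is 8.30 × (0.475 - 0.25) = +1.9 points (+1.2 at 30%, +2.1 at 70%). In the narrow gap it is +0.3, +0.4 and +0.4. It is zero if AF status is left out.

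**The case for a change.** The best case for a change is that one sentence of clarification costs little. The window really is unstated, and detection really does differ by arm. In the wide gap the arms would show -9.5 and -6.7 at 50% recurrence, and one pooled number hides that. A literal reader could put arm and AF status into one model and distort the randomised comparison by one to two points on the assumed scale.

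The gap in wording stands, and so does the caution about a joint model. Neither carries the point further.

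- It is too strong to say that no evidence rule exists: the plan's AF definition is for the whole study.
- Rhythm at the questionnaire visits is another possible reading, to which these figures do not apply.
- The sentence can be read as two comparisons by the same method, and it also allows arm as a term.
- Splitting by arm raises the standard error to about 1.3 to 1.6 times the pooled one and removes neither missed AF nor symptom selection.
- Applying one evidence rule to both arms would not equalise detection, because only the intervention arm is given the device.

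Outcome assessments also says "AF may also be captured by a 12-lead ECG, pulse check, or heart sound auscultation", two of which the study definition does not list. That may describe only how AF comes to attention. It concerns the primary endpoint and adds nothing to this contrast.

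**Conclusion.** No change is needed. The sentence leaves out detail that an analyst would fill sensibly: recurrence documented over the six months under the study's own AF definition, reported as an association, beside a randomised comparison fitted without AF status.

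Under the assumptions above the pooled contrast runs from -6.1 to -10.5 against a true -10. Most of that spread is imperfect detection as such. Adding arm moves the pooled figure by 0.2 to 0.7 points in the wide gap and by less than 0.05 in the narrow one. Under symptom selection at 30% recurrence it moves the figure away from the truth, from -10.49 to -10.78. Arm adjustment is therefore not reliably better, and the direction of any bias stays open.

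This rests on equal true recurrence in the arms, on a modest arm effect on scores, and on AF status staying out of the model for the randomised comparison. All the rates are assumed. The comparison is secondary and cannot be made causal by wording.
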